16.2 Sample size

The primary objective of this study is to examine whether there is a difference in the MMID rates post inoculation between either of the 2 FLU-v arms and placebo. A sample size of 41 subjects per arm (total 123) will provide 80% power to detect a difference in MMID rates of .70 versus .40 using a one sided 0.05 significance level. The table below shows the power that the study would have with 41 patients per arm for other MMID rates. The sample size calculations do not adjust for multiple comparisons.

Table 1. Power with 41 subjects per arm with various MMID probabilities

Probability of MMID in placebo	Probability of MMID in Vaccinated arms	Power
.70	.40	.80
.70	.44	.70
.70	.47	.60
.60	.30	.80
.60	.34	.70
.60	.37	.59
.50	.21	.81
.50	.25	.68
.50	.28	.56

In this study the main comparisons are for each of the FLU-v dose groups to placebo. The study will also compare the FLU-v dosing arms but the study will not have adequate power to detect a significant difference in MMID rates at the predicted treatment rates. This study does not control for multiple comparisons since we are trying to maintain a small sample size but yet have high power to detect the pre-defined primary objective of efficacy versus placebo when FLU-v is truly beneficial. All comparisons will be made at the one sided 0.05 significance level.

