16.6 FLU-v Secondary analysis

A secondary analysis will be performed to examine the secondary endpoints for this study. Adverse event rates between the three groups will be compared using Fishers exact test. The days of shedding, days of symptoms, number of symptoms, and FLU-PRO scores between will be examined by calculating the median and interquartile range for all three groups and then performing a two-sided Wilcoxon Rank Sum Test at the 0.05 significance level.

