16.7.2 Laboratory parameters

Time point and treatment group for absolute laboratory parameters (haematology, biochemistry, coagulation, cardiac enzymes, and thyroid function tests) will tabulate summary statistics for absolute values and changes from baseline. Laboratory values outside the normal range will be identified in subject listings.

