A randomized, double-blind, placebo-controlled efficacy and safety trial of FLU-v administered as 2 vaccinations or 1 vaccination vs placebo prior to intranasal challenge with the Influenza A 2009 H1N1 human virus.

In this study, the main efficacy comparisons are for each of the FLU-v groups to placebo. The study will not compare the two FLU-v dosing arms as the study may not have enough power to detect a significant difference in the primary efficacy endpoint of mild to moderate influenza induced disease (MMID) rates between the FLU-v groups.

2 Current Approved Study Protocol

The current approved study protocol is version 3.0 dated 18APR2017.

3 Study Hypothesis

The hypothesis is that vaccination with one dose or two doses of FLU-v + adjuvant will significantly reduce MMID when compared to individuals vaccinated with placebo.

4 Sample Size Justification and Analysis Plan

Sample size was calculated for 3 groups, a placebo group and 2 Investigational Medicinal Product (IMP) (i.e. one dose and two doses of FLU-v) groups. Each FLU-v arm will be compared to the placebo arm. Groups are randomized 1:1:1. All comparisons are at the 0.05 one-sided alpha level, and any p-value less than 0.05 would be considered as significant. This may increase the type-I error rate of potentially moving forward with an inactive treatment, but is appropriate for an early phase II trial of this type. Sample sizes assuming two different placebo MMID rates and for 80% power are given in Table 1 below.

Table 1.

Probability (rate) of MMID		Sample size per arm	Total sample size	Power	One-sided alpha
Placebo	Vaccine				
0.7	0.4	40	120	80%	0.05
0.8	0.5	37	111	80%	0.05

Table 1 shows that a sample size of 120 (40 per group) provides good power (80%) for a placebo MMID rate of 0.7 and an absolute reduction of 30%. The difference is clinically meaningful and the assumptions of a placebo MMID rate of 0.70 is reasonable and based on past experience.¹

5 Analysis Plan and Reports

The primary analysis population will be the Intent to Treat (ITT) population and will be used for the analysis of all primary and secondary endpoints. The ITT will include those participants who received both vaccination and challenge with an influenza virus.

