- Comparison of each treatment group to placebo of the proportion of asymptomatic infected subjects defined as subjects with symptom score of zero (PAI) from Day 1 post-inoculation time-point through the expected end of quarantine (Day 7) with at least one positive result for viral shedding (RT-qPCR) in any of the quarantine days from the evening of Day 1 post-inoculation.
- Summary of Adverse Events from the Post-Vaccination Diary Card
 - The number of subjects who self-reported at least once any of the adverse events listed in the Post-Vaccination Diary Card during the 21 days following first vaccination and 21 days following second vaccination. Data will be presented for each treatment group by event and according to severity (mild, moderate, severe). The number of subjects in each treatment group with no self-reported events will also be presented.

The statistical software to be used for the analyses will be SAS (version 9.4) and R (version 3.43). The analyses of the secondary binary endpoints will be performed by comparing the rates in each of the FLU-v groups to the placebo group using one-sided Fisher's exact test. For all secondary endpoints, the primary analysis will assume missing data is missing at random so missing data will be ignored.

The analysis of all continuous secondary endpoints will be performed by calculating the median and interquartile range and then performing a one-sided Wilcoxon Rank Sum Test at 0.05 level of significance. These data will be reported as tables and figures as described in sections 8-9 of this document.

Statistical analysis will be performed by a junior statistician at NIAID-NIH and will be reviewed by the senior statistician. In addition, the Senior Clinical and Scientific Leader, will repeat the statistical analysis to validate the results.

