5.8 Post-Hoc Analyses

Where possible all analyses will be prospectively planned and carried out according to this SAP. However, in the event of any significantly anomalous data or events which make any data or conclusions unreliable or scientifically questionable, then further relevant post-hoc analyses may be carried out. For example, but not limited to:

- Analysis of primary and secondary endpoints with removal of data from subjects where other respiratory infections have occurred concomitantly with the study challenge influenza virus (including 48 hours pre-inoculation and on day 2 or day 5 post-inoculation);
- Analysis of efficacy data including only subjects with an Haemagglutinin inhibition (HAI) titer for the challenge strain pre-inoculation lower than 40,
- Analysis of efficacy data comparing subjects whose HAI titer to the challenge strain rose from screening to pre-inoculation compared to those whose titer didn't change,

- Analysis with removal of data from subjects with any pre-existing heterotypic T-cell immunity to the study flu challenge virus,
- Due to the recall of atomisers in batch 160728, six subjects were inoculated with Challenge Virus with atomisers from the recalled batch, and 34 subjects were administered Challenge Virus using one atomiser per nostril rather than two atomisers per administration. Post-hoc analyses will be performed on the primary and secondary endpoints to assess whether there was any effect of the atomizer recall or/and from inoculating with one rather than two atomisers.
- Analysis of primary and secondary endpoint data (RT-qPCR and PAI) to include the data for subjects discharged from quarantine after Day 7.
- Analysis of the FLU-PRO secondary endpoint to include data for subjects discharged from quarantine after Day 7. This post-hoc analysis may also include reporting of proportion of symptomatic days and duration of symptoms for quarantine days.

6 Changes to the protocol-specified analyses

No changes to the protocol-specified analyses apart from the proposed and pre-defined post-hoc analyses.

There is a discrepancy between the sample size stated in the protocol and the sample size stated in Section 4 of this document. The protocol allowed for one additional subject per treatment group to account for unexpected subjects exclusion in the per protocol population due to a major protocol deviations.

7 References

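### SAP 5.4 tests the continuous secondary endpoints one-sided at 0.05 where the protocol's endpoint-specific text is two-sided, and SAP section 6 reports no change

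*SAP*

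**What the plan says.** **Protocol, secondary endpoints.** Section 16.6 calls for medians and interquartile ranges and then "performing a two-sided Wilcoxon Rank Sum Test at the 0.05 significance level". Section 16.4 and the synopsis say the same.

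**Protocol, general sentence.** Section 16.2, on sample size, ends with "All comparisons will be made at the one sided 0.05 significance level". The synopsis repeats it shortly before its two-sided sentence.

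**Protocol, Fisher tests.** No sidedness is given for the tests on adverse event rates.

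**SAP, secondary endpoints.** Section 5.4 specifies "performing a one-sided Wilcoxon Rank Sum Test at 0.05 level of significance" for continuous endpoints. For binary endpoints it specifies "comparing the rates in each of the FLU-v groups to the placebo group using one-sided Fisher's exact test", without naming the tail. One of these binary endpoints is the proportion of infected subjects (at least one positive RT-qPCR) whose physician-assessed symptom score is zero throughout. It is not in the protocol's list (6.2.1).

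**SAP, general sentence.** Section 4: "All comparisons are at the 0.05 one-sided alpha level, and any p-value less than 0.05 would be considered as significant".

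**SAP, adverse events.** Section 5.6 names Fisher's exact test and gives no sidedness.

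**SAP, declared changes.** Section 6: "No changes to the protocol-specified analyses apart from the proposed and pre-defined post-hoc analyses". It adds only a note on the difference in sample size. Protocol 16.4 requires departures from the protocol-specified analysis to be documented in an amendment to the protocol or the SAP.

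**Laboratory data.** Protocol 16.7.2 "will tabulate summary statistics for absolute values and changes from baseline". SAP 5.6 instead classes results as no abnormality, abnormal not clinically significant, abnormal clinically significant, or not available.

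**The concern.** The SAP uses the more permissive of two readings of the protocol for the secondary endpoints and tells its reader that nothing has changed. A favourable result with a two-sided p-value between 0.05 and 0.10 fails under the protocol's endpoint-specific rule and is called significant under the SAP. These endpoints (shedding, symptoms, FLU-PRO) would carry the argument about disease severity, so the difference affects what can be claimed.

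The asymptomatic-infected proportion raises a different problem. Protocol 12.1.1 gives the intended use as preventing infection, which would lower this proportion. Protocol 5.2 describes a mechanism that destroys cells already infected, which could leave infection detectable but silent and so raise it. A one-sided test with no stated tail can then be pointed either way after the data are seen.

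**Working it through.** **1. Reproducing the plan's own figures.** Inputs: MMID 0.70 v 0.40, one-sided 0.05, 41 per arm (Protocol 16.2). Exact power of the one-sided Fisher test is 0.813, against 0.80 stated. The other eight rows of the protocol's power table also agree within 2 points. The SAP's 40 and 37 per arm are both returned by the one-sided two-proportion formula with continuity correction. The primary design is therefore one-sided in both documents, and nothing below changes it.

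**2. Error per secondary test.** Favourable-direction error = alpha / number of sides.
- Protocol 16.6: 0.05 / 2 = 0.025, critical z = 1.960.
- SAP 5.4: 0.05 / 1 = 0.05, critical z = 1.645.
- Ratio 2.0. Total type I error is 0.05 in both cases.

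A simulation of the Wilcoxon null (41 per arm, 40,000 replicates) gave 0.0245 v 0.0495 for continuous data, and 0.0241 v 0.0489 for tied durations of 0 to 7 days (assumed distribution).

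**3. Across the family.** The SAP has seven continuous endpoints: shedding duration, AUC and peak; symptom duration, number and peak; FLU-PRO score. Seven x 2 arms = 14 tests. Expected false favourable results under the null: 14 x 0.025 = 0.35 v 14 x 0.05 = 0.70. The protocol has five such endpoints (four named in 16.6, plus viral quantitation from 6.2.1), giving 10 tests.

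The chance of at least one false favourable result was simulated with multivariate normal statistics. Correlation between the two comparisons is 0.5, because they share the placebo arm at 1:1:1. The correlation between endpoints is assumed.

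| Correlation | SAP's 7 endpoints: two-sided → one-sided | Protocol's 5 endpoints: two-sided → one-sided |
|---|---|---|
| 0.3 | 23% → 39% | 18% → 31% |
| 0.5 | 19% → 32% | 16% → 27% |
| 0.7 | 15% → 26% | 13% → 22% |

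**4. Power cost of two-sided testing.** An effect with 80% power at one-sided 0.05 has standardised mean (test-statistic) shift 1.645 + 0.842 = 2.486 before rounding error. At two-sided 0.05 its power is Φ(2.486 − 1.960) = 0.70.

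**5. Asymptomatic-infected proportion.** Let q be the placebo infection rate, which the documents do not give; the range 0.75 to 1.0 is assumed. With MMID 0.70 v 0.40, the probability of symptoms given infection is s = 0.70 / q.
- Placebo: q − 0.70.
- Vaccine that only prevents infection: (0.40 / s) x (1 − s).
- Vaccine that only prevents symptoms: q − 0.40.

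Exact one-sided Fisher power, 41 per arm:

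| q | Placebo | Infection prevented | Symptoms prevented | Power for a decrease (infection prevented) | Power for an increase (symptoms prevented) |
|---|---|---|---|---|---|
| 0.75 | 0.05 | 0.029 | 0.35 | 0.02 | 0.96 |
| 0.80 | 0.10 | 0.057 | 0.40 | 0.07 | 0.91 |
| 0.90 | 0.20 | 0.114 | 0.50 | 0.19 | 0.85 |
| 1.00 | 0.30 | 0.171 | 0.60 | 0.29 | 0.81 |

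In the opposite tail, power is below 0.002 in every row. At 0.10 v 0.40 a two-sided Fisher test has power 0.86. As an example, 4/41 v 16/41 gives p = 0.002 for an increase and p = 0.9997 for a decrease.

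**The case against.** The best defence is the protocol's own general sentence. It says, in 16.2 and in the synopsis, that all comparisons are one-sided at 0.05, and SAP section 4 repeats it, so the SAP may simply have followed it. That much stands: the protocol contradicts itself and must be reconciled too. It does not rescue section 6. The general sentence closes a discussion of MMID sample size. The two-sided wording is specific to the secondary endpoints, appears three times, and comes later in both the synopsis and section 16. Choosing between the two was a decision the SAP should have recorded.

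Four stronger readings are tempting, and the documents do not support them.
- *The overall error rate doubles.* Only the favourable-direction error does. Family-wise control was never promised either: both documents openly decline to adjust for multiplicity. Part of the 14-test figure comes from peak endpoints that the SAP added, which is why the five-endpoint figures are shown beside it.
- *Adverse events are tested only in the direction of benefit, so harm cannot show.* SAP 5.6 states neither sidedness nor direction. One-sidedness follows only by inference from the word all in section 4, and no text points the test towards benefit.
- *The asymptomatic endpoint has no valid direction because of the change from two-sided to one-sided.* It is an endpoint the SAP added, under Fisher's test, for which the protocol never fixed sidedness. A direction stated in advance would be valid; none is stated.
- *The comparison between the two FLU-v doses was dropped silently.* The SAP's opening design description says that it will not be done and gives limited power as the reason. It is missing only from section 6.

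**Conclusion.** The point holds for the continuous secondary endpoints. SAP 5.4 departs from the protocol's endpoint-specific rule and section 6 does not say so. The per-test favourable-direction error goes from 2.5% to 5%; this follows from the test definitions and needs no assumption. The family-wise figures rest on assumed correlations of 0.3 to 0.7 between endpoints and describe the scale of the effect, not the breach of a promise.

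Separately, the tail chosen for the asymptomatic-infected test decides its result. The power figures rest on the assumed q and on two pure mechanisms; a real vaccine could do some of each.

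Section 6 is also incomplete on the laboratory summaries and on the dose comparison, the latter being disclosed elsewhere in the SAP. Because the primary analysis and the sample size are untouched, this is a should-fix.

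**What to change.** - In SAP 5.4, use the two-sided 0.05 Wilcoxon test for all continuous secondary endpoints.
- Limit the general one-sided sentence to the primary MMID comparisons, in SAP section 4 and in Protocol 16.2 and the synopsis, so that the documents agree.
- State that the Fisher tests for the asymptomatic-infected proportion (SAP 5.4) and for adverse event rates (SAP 5.6) are two-sided.
- Rewrite SAP section 6 to list the actual departures: the dropped dose comparison, the laboratory summaries, the endpoints added to the protocol's list, and any sidedness that is kept different, with the reason.
- Restore the protocol's laboratory summary of absolute values and changes from baseline.

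The cost is text and one table, with no new data. One-sided secondary p-values in the favourable direction roughly double, and an effect with 80% power at one-sided 0.05 falls to about 70%. The documents do not say whether the data had been unblinded. The changes carry full weight only if made before unblinding; after it, they should be reported as corrections with their date.

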5.5 Exploratory Endpoints

- Immunogenicity of FLU-v after vaccination and influenza challenge.
 - The titer of FLU-v specific IgM and IgG antibodies in pre-vaccinated, post-vaccinated and post-challenged sera will be measured. Further isotyping of the response and functional assays may be performed. FLU-v-specific T-cell responses will be measured in PBMCs from pre-vaccination, post-vaccination and post-challenge.
- Broadness of protection of FLU-v
 - PBMCs will be exposed to at least 5 different influenza strains prior to measuring markers of T-cell activation.

The data for the exploratory analysis may be presented separately to the main clinical study report.

5.6 Safety Endpoints (pre- and post-inoculation)

- **Adverse Events:** Adverse event (AE) terms will be coded using MedDRA version 19.1. Treatment emergent AEs (TEAE) will be reported within summary presentations, by MedDRA system organ class (SOC) and preferred term (PT), and by treatment group. An AE will be classified as treatment emergent if the onset date of the AE is on or after the first administration of vaccine. In the case of partial dates being recorded, a conservative approach will be adopted for inclusion of such events within these reporting periods. If a subject experiences more than one AE with the same preferred term (within reporting period being considered) that preferred term will be counted only once in summary presentations. It will be assigned the worst observed severity and the strongest relationship to IMP among those events for summaries in which those characteristics are considered. Summary presentations will be produced for the number and percentage of subjects reporting treatment emergent AEs, AEs by severity, and AEs related to vaccine administration (by relationship). In addition, SAEs and AEs directly resulting in withdrawal from study will be summarised. Summaries

will be separated into pre-inoculation (events reported from the time of first vaccination up to Day 0 prior to time of inoculation) and post-inoculation (Day 0 inoculation time through study completion). AE rates, evaluated between groups to placebo, will be performed using Fishers exact test.

- **Laboratory parameters:** Laboratory parameters (haematology, biochemistry, cardiac enzymes, coagulation and urinalysis) will be presented as a comparison of treatment groups and placebo by No abnormality detected, Abnormal Not Clinically Significant (NCS), Abnormal Clinically Significant (CS) and Not Available. Laboratory values outside the normal range will be identified in subject listings.
- **Physical Examination:** Physical examination findings (Complete Physical Exam and Directed Physical Exam) will be included within subject listings.
- **Concomitant medication:** Concomitant medication terms will be coded using the WHO Drug Dictionary Enhanced version 2016:3 (September 1, 2016). Medications will be assigned as being prior to vaccine administration (IMP dosing), or concomitant with IMP dosing based on start and stop dates of the medication and the timing of receiving IMP. If the medication stop date is before the date of IMP (when applicable), the medication will be assigned as being prior to IMP. In all other situations, the medication will be assigned as being concomitant with IMP. Prior and concomitant medications (separately identified) will be included in subject listings.

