6.4.1 Safety endpoints

- Incidence of treatment-emergent AEs (TEAE), severity, seriousness and causality
- Absolute values and change from baseline in routine clinical and laboratory parameters
- Vaccine Related Physical examination findings
- Concomitant medications.

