15.2.8 Laboratory values

Deterioration in a laboratory value (compared to baseline) should only be reported as an AE if the deterioration fulfils the criteria for an AE and it is clinically significant in the opinion of the

Investigator. If deterioration in a laboratory result is associated with clinical signs and symptoms, the sign or symptom will be reported as an AE and the associated laboratory result will be considered as additional information.

The Investigator will judge whether abnormal laboratory values are clinically significant or not clinically significant, and record this in the source document. This entry should be signed and dated by the relevant investigator. Laboratory abnormalities detected at screening will be considered as part of the medical history and will not be reported as AEs.

Challenge Virus associated laboratory abnormalities (e.g., elevated ALT, AST or GGT; decreased neutrophils) may be recorded as AEs (at the discretion of the Investigator).

Any laboratory abnormality that meet the criteria of a Grade 2 AE or above will be discussed with the SME. If a Grade 3 laboratory abnormality occurs (not related to Viral Challenge), a confirmatory test should be performed, preferably within 48 hours (if practically feasible) after the results have become available.

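### The SAP replaces the protocol's summaries of laboratory values and changes from baseline with abnormality categories, and does not declare the change

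*SAP*

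**What the plan says.** **Protocol.** Section 6.4.1 (and the synopsis) names as a safety endpoint "Absolute values and change from baseline in routine clinical and laboratory parameters". Section 16.7.2 gives the laboratory method. Its sentence is awkwardly built, but it can only mean that, by time point and treatment group, the report "will tabulate summary statistics for absolute values and changes from baseline". The panels it names are "haematology, biochemistry, coagulation, cardiac enzymes, and thyroid function tests". Section 13.1 sets baseline as the measurement before study vaccine. Section 16.4 says that departures from the specified analysis will be documented in a protocol or SAP amendment, and that the SAP will describe all baseline assessments.

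**SAP.** Section 5.6 names a different set of panels, "haematology, biochemistry, cardiac enzymes, coagulation and urinalysis", and presents them by treatment group as "No abnormality detected, Abnormal Not Clinically Significant (NCS), Abnormal Clinically Significant (CS) and Not Available". It adds: "Laboratory values outside the normal range will be identified in subject listings". It mentions no absolute value, change from baseline, baseline definition or time point for laboratory data. The table list contains one laboratory table, 14.3.3, titled as an overall summary. ECG, spirometry and vital signs appear only as listings 16.2.8.3 to 16.2.8.5, and no figure covers safety measurements. Section 6 states: "No changes to the protocol-specified analyses apart from the proposed and pre-defined post-hoc analyses". Its only other disclosure is the sample-size discrepancy.

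**The concern.** A safety endpoint that the protocol defines on the measurement scale is analysed in the SAP on a coarse category scale, and the SAP's own statement of changes does not mention it.

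The two scales answer different questions. Means, medians and changes from baseline by arm and visit show whether a vaccine arm moves as a group, and by how much. Category counts show only how many subjects left the normal range and whether the investigator thought it mattered. In healthy volunteers a modest vaccine effect on, say, a liver enzyme or a cell count could lie wholly inside the normal range and leave every category count unchanged.

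Timing matters as well. Protocol 15.2.8 recognises that the challenge virus itself may raise liver enzymes or lower neutrophils. A summary that does not separate visits before and after challenge may mix the vaccine's effect with the virus's. SAP 5.6 makes that split for adverse events but states none for laboratory data.

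Also at stake is the reliability of SAP Section 6, which readers use to see where the analysis departs from the protocol.

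**Working it through.** No arithmetic applies: the point depends on no sample size, power or event count. The check sets the two documents side by side.

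| Item | Protocol | SAP |
|---|---|---|
| Laboratory summary | Absolute values and changes from baseline (6.4.1, 16.7.2) | Four abnormality categories (5.6) |
| By treatment group | Yes (16.7.2) | Yes (5.6) |
| By time point | Yes (16.7.2) | Not stated (5.6) |
| Baseline | Before study vaccine (13.1) | None given for laboratory data |
| Out-of-range values | Listed (16.7.2) | Listed (5.6) |
| Vital signs, ECG | Within the routine clinical parameters of 6.4.1; no method in 16.7 | Listings only |
| Panels | Haematology, biochemistry, coagulation, cardiac enzymes, thyroid (16.7.2) | Haematology, biochemistry, cardiac enzymes, coagulation, urinalysis (5.6) |
| Declared change | Must be documented (16.4) | None for laboratory data (6) |

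**Step 1: is the laboratory summary lost?** The listing sentence is common to both documents, so it does not replace the tabulation. The remaining SAP content is the four-category comparison. No table title names absolute values or changes. Individual results may still be printed in listings 16.2.9.2 and 16.2.9.3, so the data survive; what disappears from the specification is the summary.

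**Step 2: is the change declared?** Section 6 excepts only the post-hoc analyses. Section 5.8 gives its post-hoc analyses as examples, and none concerns laboratory data. The sample-size note does not cover it either. For laboratory data the declaration is therefore incorrect.

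**Step 3: does another summary fill the gap?** Adverse event tables do not. Under Protocol 15.2.8 a laboratory deterioration is reported as an adverse event only if it meets the adverse event criteria and is clinically significant in the investigator's opinion. A shift inside the normal range would normally enter no table, and the size of a shift outside it would not be tabulated.

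**Step 4: vital signs and ECG.** Protocol 16.7 has subsections for adverse events, laboratory parameters, physical examination and concomitant medications. It specifies no analysis of vital signs or ECG. The SAP supplies none. Here the endpoint lacks a summary in both documents.

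**Step 5: panel lists.** The Time and Events schedule shows haematology, biochemistry (including creatine kinase and total protein) and urinalysis. It shows no coagulation or thyroid tests, and the SAP has no listing named for either. The SAP also drops thyroid and adds urinalysis relative to Protocol 16.7.2, without comment.

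**The case against.** The strongest reply is that the SAP does analyse laboratory data. There is a by-arm table, its shell is in a separate document that cannot be checked here, and full listings exist. A reader might infer that the endpoint has no analysis at all, and the documents do not support that. The shell could even contain value summaries. It would then go beyond the SAP text, which does not ask for them, so the gap in the specification stands.

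Second, the categories are not wholly the investigator's opinion. Protocol 15.2.8 says "The Investigator will judge whether abnormal laboratory values are clinically significant or not clinically significant", but whether a value is abnormal is set by the laboratory's normal ranges and the DMID grading table (Protocol 14). A vaccine effect that pushed more subjects out of range would show as fewer normal results and more abnormal ones. It would be wrong to say the table cannot show a shift between arms; it misses shifts within range, and the size of all shifts.

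Third, a reader might infer that the SAP dropped an analysis of vital signs and ECG. It did not, because the protocol never specified one. On these measurements Section 6 is not false; the endpoint was simply left without a method.

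Fourth, absence from the schedule does not prove that coagulation and thyroid tests are never done. Protocol 14.1.2 says testing is not limited to the named panels, refers to a laboratory analytical plan, and allows extra tests at the investigator's discretion. The SAP has a listing for unscheduled and other safety tests (16.2.9.4). The lists need reconciling, and the documents do not justify simple deletion.

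Fifth, a link to dose selection for Part B is tempting, since the optimal dose is to be judged on efficacy and safety. But Part B is only a possible later amendment, conditional on significant efficacy, and nothing says the choice would rest on laboratory means.

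**Conclusion.** The point holds for laboratory data. The protocol specifies summaries of absolute values and changes from baseline by time point and arm, the SAP specifies abnormality categories instead, and SAP Section 6 wrongly reports no such change. For vital signs and ECG it holds in a different form: the endpoint in Protocol 6.4.1 has no summary analysis in either document.

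The consequence is limited to descriptive safety reporting and to the transparency of the SAP. Neither the efficacy analyses nor the sample size is affected, and the underlying data are still collected and listed. The conclusion rests on the SAP text and table list; it assumes that the unseen shell for Table 14.3.3 does not add what SAP 5.6 omits. If it does, SAP 5.6 still needs to say so. The change should be made, because it is cheap and restores an endpoint the protocol names.

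**What to change.** 1. In SAP 5.6 and the table list, restore summaries of absolute value and change from the pre-vaccination baseline, by visit and arm, for scheduled haematology and biochemistry, including creatine kinase. State the baseline rule from Protocol 13.1.
2. Add the same summaries for vital signs and ECG, so that the clinical half of the 6.4.1 endpoint has an analysis.
3. Keep the four-category table as a supplement. It remains the natural format for dipstick urinalysis.
4. Correct SAP Section 6 so that it discloses and justifies any laboratory summary specified by the protocol that will not be produced. Disclosure alone would cure the inconsistency with Protocol 16.4, but would not give the endpoint its summary.
5. Reconcile the panel lists in Protocol 16.7.2 and SAP 5.6 with the Time and Events schedule. For coagulation and thyroid, either confirm that results are collected and where they will be shown, or remove them from the analysis text.

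Cost: a set of standard descriptive tables, repeated over analytes and visits, and some SAP text. No new data or extra visits are needed.
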